2.6 Timeline

Study Time Commitment

Stage	Time (mins)	Description
Recruitment	10	Via email, flyer and/or class presentation
Familiarization Session	35	Familiarize test subject with the purpose of the study, all experimental devices and the timeline of each experimental condition
Experimental Visits	255	All measurements, single visit
Total	300	

Familiarization Session	
Time (mins)	Action
0:00-5:00	Share adult consent form with participant. Questions and concerns will be heard on the protocol and purpose of this study.
5:00-10:00	Discuss the underlying physiology and purpose that lead to the creation of this study. Discuss how this study will answer the research questions.
10:00-30:00	The researcher will attach each device to the participant to familiarize him/her to the protocol . No data will be collected for later analysis during this period.
30:00-35:00	Subject and researchers will schedule the date and time for CON and SMS. ActiGraph will be attached to the research participant. A document will be provided detailing all behavioral restrictions (e.g. abstinence from caffeine, alcohol) and instructions on wearing the ActiGraph will be provided.
Session End – Total time spent in APL: 35 minutes	

[figure not shown]
CON Experimental Session			
Time (mins)	Action	Measurement Order	EXAMPLE START TIME
-30:00 - -25:00	Anthropometrics	Weight (kg) Height (cm) BMI (kg/m ²)	10:15 AM
-25:00	Begin Supine Rest	N/A	10:20 AM
-25:00 - -15:00	Affix devices to participant.	Path lengths (cm)	10:20 AM
-15:00	End Supine Rest. Begin continuous data collection from devices. Begin sitting period	TCD measures NIRS measures NIBP measures	10:30 AM
-15:00 - -5:00	Ultrasound data collection	Cerebrovascular blood flow (common carotid, internal carotid, and vertebral arteries)	10:30 AM
-15:00 - -5:00	VICORDER® data collection	bfPWV/A cfPWV/A faPWV/A	10:30 AM
-5:00-0:00	Mental Arithmetic Test	N/A	10:40 AM
00:00-1:00	VICORDER® data collection	bfPWV/A immediately after MAT	10:45 AM
5:00-20:00	VICORDER® data collection	bfPWV/A every 5m post-MAT for addition 20m	10:50 AM
25:00-30:00	VICORDER® data collection	All measures of PWV/A 10m post-MAT	11:10 AM
30:00-40:00	Cognitive tests	Trails A+B VFT	11:15 AM
Test End – Total time spent in APL: 75 minutes			

[figure not shown]
[figure not shown]
SMS Experimental Session

Time (mins)	Action	Measurement Order	EXAMPLE START TIME
-140:00 - -135:00	Anthropometrics	Weight (kg) Height (cm) BMI (kg/m ²)	8:25 AM
-135:00	Begin Supine Rest	N/A	8:30 AM
-135:00 - -125:00	Affix devices to participant. Collect path lengths required for measures from PWV/A	Path lengths (cm)	8:30 AM
-125:00	End Supine Rest. Begin continuous data collection from devices. Begin prolonged sitting period	TCD measures NIRS measures NIBP measures	8:40 AM
-120:00 -115:00	Ultrasound data collection	Cerebrovascular blood flow (common carotid, internal carotid, and vertebral arteries)	8:45 AM
-115:00 - -110:00	VICORDER® data collection	bfPWV/A cfPWV/A faPWV/A	8:50 AM
-20:00 - -15:00	Ultrasound data collection	Cerebrovascular blood flow (common carotid, internal carotid, and vertebral arteries)	10:25 AM
-15:00 - -5:00	VICORDER® data collection	bfPWV/A cfPWV/A faPWV/A	10:30 AM
-5:00	End prolonged sitting period	N/A	10:40 AM
-5:00 – 0:00	Mental Arithmetic Test	N/A	10:40 AM
00:00-1:00	VICORDER® data collection	bfPWV/A immediately after MAT	10:45 AM
5:00-20:00	VICORDER® data collection	bfPWV/A every 5m post-MAT for addition 20m	10:50 AM
25:00-30:00	VICORDER® data collection	All measures of PWV/A 10m post-MAT	11:10 AM
30:00-40:00	Cognitive tests	Trails A+B VFT	11:15 AM
Test End – Total time spent in APL: 180 minutes			

[figure not shown]

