The Combined Effects of Prolonged Sitting and Mental Stress on Vascular and Cerebrovascular Function in Middle-Aged Adults

NCT number NCT04207333

Document Date 12/19/2019

MASTER PROTOCOL

The Combined Effects of Prolonged Sitting and Mental Stress on Vascular and Cerebrovascular Function in Middle-Aged Adults

Principal Investigator

[name]
Department of Exercise & Sport Science
[name],
UNC-CH
[name]

Co-Investigator(s)

[name]
[name]

Funding Source: None

Version Date: 12/19/2019

PROTOCOL SYNOPSIS	
Study Title:	The Combined Effects of Prolonged Sitting and Mental Stress on Vascular and Cerebrovascular Function in Middle-Aged Adults
Funding	UNC Department of Exercise & Sport Science
Clinical Phase	Pilot Testing
Study Rationale	Prolonged sitting may pose a public health risk through its effects on the cardiovascular system, and may lead to impaired whole-body cardiovascular health, which includes both vascular and cerebrovascular function. These effects may interact with other environmental variables, such as stress. However, no study has investigated the combined effect of a mental stressor and prolonged sitting on vascular and cerebrovascular function. The combined effect of prolonged sitting and mental stress may lead to an exacerbated effect on vascular, cerebrovascular, and executive function. We hypothesize that mental stress with the addition of prolonged sitting [SMS] will result in a greater increase in peripheral, central and cerebral arterial stiffness and elicit a decrease in cerebral perfusion, total blood flow to the brain, middle cerebral artery velocity and executive function, compared to mental stress without prolonged sitting [CON]. The findings from this study may result in a public health message regarding sedentary behavior and stress, and will help elucidate the mechanisms behind acute vascular, cerebrovascular, and cognitive dysfunction during prolonged sitting.
Study Objective(s)	To examine the cardiovascular response to mental stress with or without previous exposure to a bout of prolonged sitting.
Study Design	Randomized Crossover Design, with two experimental conditions: without prolonged sitting + stress [CON] and with prolonged sitting + stress [SMS].

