2.2 Allocation to Treatment Groups and Blinding

The randomization procedure will be performed by a research assistant. Participants will be randomized into either CON or SMS intervention for the first visit. This will be done during the familiarization session using an online randomization software (www.randomizer.org).

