2.3 Experimental Design

Study Design

This study is a multi-visit (three in total) randomized crossover trial.

Overview

During a single familiarization session, the research team will obtain informed consent, and will describe to participants the purposes and procedures of this study. They will then be exposed to all experimental devices on in a quiet, dimly lit and environmentally controlled room.

Participants will return to the same location for two experimental conditions following these pre-assessment guidelines:

- Fasted (> 12 hours), consuming only water.
- No caffeine consumption 12 hours prior to testing.
- No vigorous exercise 24 hours prior to testing.
- No alcohol consumption 24 hours prior to testing.

Table 1. Study Variables

Type	Measure
Independent (Conditions)	Control (CON): Exposure to MS without PS Sitting-Mental Stress (SMS): Exposure to MS after period of PS
Primary Outcomes	Brain PWV Brachial-femoral PWV
Secondary Outcomes	Executive function Neurovascular coupling Carotid-femoral PWV Augmentation index Femoral-ankle PWV

Experimental Set-Up

[figure not shown]

Figure 1. Experimental setup for to assess full body cardiovascular health. Each experimental device responsible for collecting data is shown in this picture and close ups.

Familiarization

Participants will be familiarized with all experimental procedures and then given the opportunity to ask any questions prior to providing written consents. Subjects will be brought to an upright, seated position using an Armedica AM353 Hi-lo Treatment Table (Tiger Medical, TIGER#TM83695) with feet flat on the ground with approximately 90 degrees of knee flexion. If feet cannot touch the ground, a platform will be used. The angle of recline of the chair will be measured, as well as the distance from the bottom of the chair to the ground to ensure equivalent chair placement for the second visit.

Experimental Visits

Refer to both *Table 1* and *Figure 1* for a breakdown of when experimental measures will be taken through both visits.

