11.3	7814																																																																																																																																																																																																						
15.0	7807																																																																																																																																																																																																						
18.8	7800																																																																																																																																																																																																						
22.5	7793																																																																																																																																																																																																						

 Test duration: Approximately 5min Participant is in seated upright position At the beginning of the test, the researcher will call out a four digit number and ask the participant to subtract either 7 or 13 Correct responses will not be recorded as an outcome for this study 																																																																																																																																																																																																							

The MS used for this protocol is the Mental Arithmetic Test (MAT), a commonly used exam to impose a small psychological stimulus on the participant. This test will approximately last for five minutes. The researcher will call out a four-digit number and ask the participant to subtract either seven or 13. Correct responses will not be recorded as an outcome for this study. During this test a metronome will play at a pre-set tempo. The subjects will be required to conduct continuous subtraction with the tempo to the best of their ability. Every minute, a new four digit number will be called out and the participant must subtract the seven or 13 from the number.

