Alternating fluency		Rapid generation of words by alternating between two semantically unrelated categories. "Fruit and furniture" are often used.	
Excluded-letter fluency		Rapid generation of words that do not contain a specified vowel (e.g., the letter "A").	

Cognitive Measurement 3: Memory Recall

Participants will be read word lists from the Hopkins Verbal Learning Test at the rate of 1 word every 2 seconds pre-test and post- cognitive testing period. The Hopkins Verbal Learning test word lists contain 12 words, 4 words from 3 semantic categories.

Cognitive Measurement 4: Brain Fog

Brain fog will be subjectively measured using a modified Borg Rate of Perceived Exertion (RPE) scale as there is no known reliable and valid objective measure of brain fog. This will be administered pre-test and post-cognitive testing period.

Data Reduction

The data collection periods are listed in Table 3. Minute values are noted in **Figure 1** and are expressed relative to the administration of the MAT.

Table 3. Data reduction methods for experimental protocol

Device	Outcomes	CON (min)	SMS (min)	Reduction
VICORDER®	bfPWV	-5, 0, 5, 10, 15, 20, 25	-115, -15, 0, 5, 10, 15, 20, 25	Measures done in triplicate. Closest 2 will be averaged for mean and variance reported
	cfPWV	-5, 25	-115, -15, 25	
	faPWV	-5, 25	-115, -15, 25	
	CBPs	-5, 0, 5, 10, 15, 20, 25	-115, -15, 0, 5, 10, 15, 20, 25	
	Peripheral BPs	-5, 0, 5, 10, 15, 20, 25	-115, -15, 0, 5, 10, 15, 20, 25	
	Augmentation index	-5, 0, 5, 10, 15, 20, 25	-115, -15, 0, 5, 10, 15, 20, 25	
TCD	Brain PWV	Continuous	Continuous	30s selections made by following a
	MCA velocity	Continuous	Continuous	

	Static cerebral autoregulation	Continuous	Continuous	prearranged protocol. Data for the outcome in the time epoch will be averaged and SD will be reported
	Neurovascular coupling	Continuous	Continuous	
NIBP	Baroreflex sensitivity	Continuous	Continuous	30s selections made by following a prearranged protocol. Data for the outcome in the time epoch will be averaged and SD will be reported
	Heart rate variability	Continuous	Continuous	
	Heart rate	Continuous	Continuous	
Ultrasound	Cerebrovascular BF	-5, 25	-120, -5, 20	
NIRS	Cerebral perfusion	Continuous	Continuous	30s selections made by following a prearranged protocol. Data for the outcome in the time epoch will be averaged and SD will be reported
	Tissue saturation index	Continuous	Continuous	
	Venous pooling	Continuous	Continuous	

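### Participants are briefed on the study's physiology and purpose before both visits and cannot be masked to sitting; if the briefing conveys the expected direction, expectancy could bias executive function.

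*Combined protocol and SAP*

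**What the plan says.** The Familiarization Session table in section 2.6 gives minutes 0 to 5 to the consent form and questions. Minutes 5 to 10 are a separate item: "Discuss the underlying physiology and purpose that lead to the creation of this study", then "Discuss how this study will answer the research questions". The overview in section 2.3 likewise says that the team "will describe to participants the purposes and procedures of this study" at this session. Section 9.1 promises a full explanation before enrolment.

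The Study Rationale in the synopsis is directional. Compared with CON, SMS is expected to "elicit a decrease in cerebral perfusion, total blood flow to the brain, middle cerebral artery velocity and executive function". Section 1 also links sedentary behaviour to poorer executive function.

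Section 2.2 has blinding in its heading, but its text covers only allocation: "Participants will be randomized into either CON or SMS intervention for the first visit". Section 2.3 sets 20 minutes of sitting in CON against 2 hours in SMS.

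Executive function is a secondary outcome (sections 2.3 and 4.1), measured by Trails A and B in seconds and by verbal fluency word counts (section 2.5). Table 3 gives one score per test per visit, and Table 4 places it after the stressor only. Section 2.5 adds a further measure: "Brain fog will be subjectively measured using a modified Borg Rate of Perceived Exertion (RPE) scale".

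**The concern.** A participant always knows how long he or she sat, so condition cannot be masked. What can still be protected is the participant's ignorance of which visit is expected to go worse. The plan sets aside time to explain why the study exists and how it will settle its questions, and specifies no neutral wording.

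Trails and verbal fluency depend on effort. Someone who expects to do worse after long sitting may try less hard or give up sooner on that visit. The result would be slower Trails times and fewer words in SMS, which is the hypothesised pattern. A CON versus SMS difference in executive function could then not be read as an effect of sitting alone. Once a participant has been briefed, no analysis can undo it, so the change has to come before enrolment.

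**Working it through.** **1. Is there a figure in the plan to reproduce?** Not for this point. The only design figure is the approximately 18 participants in section 4.6, which is built on pulse wave velocity: change 1 m/s, error 1.25 m/s, both error rates 5%. Taking 1.25 as the SD of the paired difference and a one-sided 5% level, n = [1.25 × (1.645 + 1.645) / 1]² = 16.9, so 17, or 19 by the exact noncentral t. This agrees with 18 to within rounding of method. It says nothing about executive function or expectancy.

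**2. Could a participant tell the conditions apart?** Yes. Sitting lasts 20 minutes or 2 hours (section 2.3), and time in the laboratory is 75 or 180 minutes (section 2.6). The CON and SMS dates are booked with the participant at the end of familiarization (section 2.6).

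**3. Does the plan contain any mitigation?** None was found. No section withholds the hypothesis, fixes a neutral script or measures expectancy. Section 4.5 has a single observer for each outcome and does not mention masking.

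**4. Does the crossover remove the bias?** Write a participant's score as

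score = person + period + τ (if SMS) + e (if SMS) + error,

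where τ is the true effect of sitting and e is the expectancy shift. The within-person SMS minus CON difference removes the person term. Averaging over the two visit orders in equal numbers removes the period term. What remains is τ + e. Random order balances period, but e travels with condition and stays.

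**5. What would e do to the error rate?** The documents give no value for e, so this is an illustration over an assumed range. Inputs: n = 20 (section 2.1), with n = 18 (section 4.6) for comparison; α = 0.05 (section 4.2, sidedness not stated, two-sided assumed); τ = 0; and δ = e divided by the SD of the paired difference. With one score per visit, the mixed model is approximated by a paired t-test. The statistic follows a noncentral t with n − 1 degrees of freedom and noncentrality δ√n. It is significant when it exceeds 2.093 in absolute value (n = 20) or 2.110 (n = 18).

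| Assumed δ | δ√20 | P(significant), n = 20 | P(significant), n = 18 |
|---|---|---|---|
| 0 | 0 | 5.0% | 5.0% |
| 0.1 | 0.447 | 7.1% | 6.9% |
| 0.2 | 0.894 | 13.6% | 12.6% |
| 0.3 | 1.342 | 24.7% | 22.5% |
| 0.4 | 1.789 | 39.7% | 36.0% |

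Almost all of the false positives fall in the hypothesised direction: at δ = 0.2 and n = 20, 13.3 of the 13.6 percentage points.

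**The case against.** The strongest objection is that the documents never say participants are told the expected direction. The objective and aims (sections 1.1 and 1.2) are neutral, the directional hypothesis stands in the synopsis, and no briefing script is shown. This stands, and it is why the point is conditional. It does not dispose of the point: five minutes on the physiology behind a study whose rationale is harm from sitting is hard to deliver neutrally, and the plan does not require neutrality.

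Four stronger readings are tempting, and the documents do not support them.

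- **Brain fog moves as hypothesised.** Brain fog is in no hypothesis, outcome list, results table or session timetable. As a self-rating it is exposed, but an expectation of harm would raise it, and no planned test uses it.
- **The primary outcomes are biased.** Both are device-measured pulse wave velocities. The stressor does depend on effort ("The subjects will be required to conduct continuous subtraction with the tempo to the best of their ability"), but nothing shows whether expectancy would raise or lower effort or arousal, or by how much. The route is speculative.
- **A baseline score would separate expectancy from sitting.** If expectancy acts on the post-stressor score, the change from baseline still contains τ + e. The missing baseline is a different matter.
- **The error rates in the table describe this trial.** They follow from assumed shifts and show only how sensitive the test is.

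It is also fair to say that the study is labelled pilot testing, that its title already names sitting and stress, and that withholding the rationale is a disclosure decision for the ethics board and more than a change of wording. These limit what the fix can achieve, but they are not reasons to keep the briefing as it is.

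**Conclusion.** The point holds conditionally, for one secondary outcome. The plan schedules a purpose-and-mechanism briefing before both visits, the condition is unmaskable, and nothing guards against disclosing the expected direction. If the direction is conveyed, which is likely but not stated, executive function could be biased in the hypothesised direction, and randomising the order would not correct it.

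The size is unknown. The 7% to 40% range assumes a shift of 0.1 to 0.4 SD of the paired difference, no true effect, 20 complete pairs and a two-sided 5% test. It should not be quoted as an estimate. The sample size and the primary outcomes are not called into question. The change is worth making before enrolment because it is cheap and the bias cannot be repaired afterwards.

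**What to change.** - **Section 2.6:** replace the 5 to 10 minute item with a fixed neutral script. It should cover the procedures, the risks, and the fact that responses to a mental task are compared after a shorter and a longer seated period. It should give no mechanism and no expected direction.
- **Sections 2.3 and 9.1:** use the same neutral wording where the purpose is described and the full explanation is given, subject to ethics approval. Otherwise these sections would contradict the script.
- **Section 5.3:** this schedules only thanks and a discussion of results. Extend it to cover the physiology and the hypotheses once the participant has completed the study.
- **Limitation:** state for executive function that participants knew their condition, so expectancy is reduced rather than eliminated.

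Cost: revised script and consent wording, ethics approval, and a less detailed rationale up front. No extra staff, visits or procedures are needed.

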1 BACKGROUND AND RATIONALE

Introduction and Rationale

Prolonged sitting (PS) has gained attention over the past decade due to the sitting epidemic that takes place in the workplace.^{1,2} Participating in a sedentary lifestyle is common due to occupation, technology and vehicle transportation. Sedentary behavior (SB) has been shown to be a risk factor for cardiovascular disease (CVD) and all-cause mortality. Additionally, a sedentary lifestyle has been linked to chronic cognitive dysfunction, thus playing a role in the appearance of Alzheimer's Disease and Related Dementia's (ADRD)³. The available research demonstrates that chronic SB is associated with a reduction in brain volume⁴ and a decline in cognition, in particular executive function (EF)^{5,6}. Although, there is a level of uncertainty in the mechanism(s) connecting repeated acute SB exposure to chronic cerebrovascular complications.

In addition to cerebrovascular implications as a result of sedentarism and stress, central and peripheral cardiovascular function and structure are disrupted⁷⁻⁹. In contrast to our understanding of cerebrovascular function, the physiological mechanisms in which a mental stressor or a sedentary behavior like PS¹⁰⁻¹² impact systemic cardiovascular function is better understood. Pooling of blood in the lower-limbs is the first cardiovascular disruption as a result of PS that eventually leads to failures in regulatory mechanism that maintain healthy function^{11,13-15}. Repeated activation of neurohormonal pathways due to mental stress is known to impair cardiovascular health^{16,17}. It is less clear how these negative stimuli impact the CVS acutely when experienced in combination. Developing our knowledge on the topic of cerebrovascular and vascular health is necessary to develop societal and behavioral solutions for the sedentarism and stress epidemics that significantly burden our healthcare system¹⁸⁻²⁰ and economic productivity²¹. This study will provide new insights on the physiological mechanisms these health behaviors take to negatively change the responses of the CVS.

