Participants will arrive to the Applied Physiology Laboratory (APL) between 6:00 and 10:00 AM fasted (for Visit 3: 2-5 days following the Visit 2). Participants will be fasted and refrain from caffeine intake for at least 12 hours, and alcohol and strenuous physical activity for at least 24 hours prior to arrival. Upon arrival, height and weight will be recorded followed by 10 minutes of quiet rest in the supine position (white solid boxes in **Figure 1**). During these 10 minutes, the subject will be fitted with a NIRS probe on the prefrontal cortex and medial gastrocnemius. The NIBP, TCD, and VICORDER® devices will also be affixed to the participant during this time period during this time. Sitting periods (solid gray boxes in **Figure 1**) will begin for both conditions once all devices are attached to the participant, the subject is shifted to an upright seated position, and at least 10min of supine rest has been recorded. During the CON visit, subjects will undergo a brief 20min sitting period. For the SMS condition, subjects will be asked to sit still and quietly for 2 hours while watching a non-stimulating documentary. Each condition will receive the MS (black boxes in **Figure 1**) at the conclusion of the sitting periods in both CON and SMS. After exposure to the MS in both conditions, data collection procedures for this protocol will be completed for VICORDER® immediately after the MS and every 5 minutes for 25 minutes (See **Figure 1** for visual details on how and when data is being collected). Brain BF will be assessed by US 20 minutes post-completion of the MAT. Finally, a battery of cognitive tests (Verbal Fluency Test and Trails A+B tests) will be administered to the participant (boxes with diagonal shades in **Figure 1**).

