4.2 Statistical Analysis

All statistical procedures will be completed with SPSS Statistics version 25.0 (SPSS, IN., Durham, NC, USA) and Jamovi v0.9 (Jamovi, UK). The α -level will be set a prior at 0.05 for all statistical procedures. Descriptive statistics and mechanistic outcomes will be collected to compare similarities amongst the sample group and to eliminate the potential for extraneous covariates. Answering the research question will require a linear multi-level mixed model. Statistical models will observe for changes in the primary and secondary outcomes within conditions (Baseline, Post-PS, Post-MS) and between conditions (CON vs. SMS at similar time points). Mechanistic outcomes will also be used to assist in discussions of physiological responses to MS and PS. Effect sizes will be calculated as Cohen's d , where <0.20 is considered to be a small, > 0.20 to < 0.50 a moderate, and > 0.60 a large effect. For the mixed models Cohen's d will be calculated as the effect of condition (β) or time (β) from linear mixed models divided by the baseline SD. Raw data will be presented as mean [standard deviation] and mixed model data are presented as mean [95% confidence interval].

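### The CON timetable allows 10 minutes of sitting before the arithmetic test where section 2.3 specifies 20, which puts CON's only pre-stress VICORDER reading within 10 minutes of the posture shift if staff follow the timetable

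*Combined protocol and SAP*

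**What the plan says.** Section 2.3 (Experimental Visits) starts the sitting period once the participant is upright, after at least 10 minutes of supine rest. It then sets the two durations. For CON: "During the CON visit, subjects will undergo a brief 20min sitting period". For SMS: "subjects will be asked to sit still and quietly for 2 hours while watching a non-stimulating documentary". The stressor comes "at the conclusion of the sitting periods in both CON and SMS".

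The CON timetable in section 2.6 places "End Supine Rest. Begin continuous data collection from devices. Begin sitting period" at -15:00 (10:30 AM) and the Mental Arithmetic Test at -5:00 (10:40 AM). Between them, ultrasound and VICORDER each have a row covering the same interval, -15:00 to -5:00. The SMS timetable places "Begin prolonged sitting period" at -125:00 (8:40 AM), the first VICORDER set at -115:00, a second at -15:00, and the test at -5:00.

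Tables 2 and 3 list one pre-stress VICORDER time in CON (-5) and two in SMS (-115 and -15). Section 4.2 has the models look at change across baseline, post-sitting and post-stress within a condition, and compare the conditions at like time points. It does not say which SMS reading the single CON pre-stress reading is paired with.

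**The concern.** Sections 2.3 and 2.6 describe two different control conditions, and staff cannot deliver both. The sitting period is the experimental factor, so its length in the control arm is part of the intervention and not a label.

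The timetable version also leaves little or no settling time before the pre-stress reading. In CON that one reading is the starting value for brachial-femoral PWV (primary), carotid-femoral PWV, femoral-ankle PWV, central pressures, peripheral pressures and augmentation index. If pressures or PWV are still adjusting to the upright posture when it is taken, CON's pre-to-post-stress change contains some posture effect, and not necessarily the same amount as in SMS. Brain PWV is less exposed because it is recorded continuously and a late epoch can be chosen. In CON, however, even the latest epoch before the test is at most 10 minutes after the shift.

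**Working it through.** All times are in minutes relative to the end of the arithmetic test (Figure 2 legend). The inputs are the timetable rows in section 2.6 and the durations in section 2.3.

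**Reproducing the SMS figure.** Sitting before the test = -5 - (-125) = 120 min. The clock times, 8:40 to 10:40, also give 120. This is the 2 hours of section 2.3.

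**The same subtraction for CON.** -5 - (-15) = 10 min. The clock times, 10:30 to 10:40, also give 10. Section 2.3 says 20.

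Two other ways of counting were tried:
- Including the 5-minute test: 0 - (-15) = 15 min, still not 20.
- Counting from the start of supine rest: -5 - (-25) = 20 min. This matches the number, but section 2.3 starts the sitting period at the upright shift, so supine rest does not count.

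**Pre-stress VICORDER rows, in minutes after the supine-to-seated shift.**

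| Row | Start | End |
|---|---|---|
| CON, only set | -15 - (-15) = 0 | -5 - (-15) = 10 |
| SMS, first set | -115 - (-125) = 10 | -110 - (-125) = 15 |
| SMS, second set | -15 - (-125) = 110 | -5 - (-125) = 120 |

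**Can a full CON set match the first SMS set within the timetable?** Assume a CON set takes 5 minutes, as the first SMS row allows for all three arterial segments. Ten minutes of settling plus 5 of measurement is 15 minutes, and CON has 10. The latest full set runs from -10 to -5, which is 5 to 10 minutes after the shift. The same interval results if ultrasound takes the first 5 minutes of the shared window, which is the time it is given in SMS.

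**With the 20 minutes of section 2.3.** Sitting starts at -5 - 20 = -25.
- Ultrasound at -20 starts -20 - (-25) = 5 min after the shift. The first SMS ultrasound starts at -120 - (-125) = 5.
- VICORDER at -15 starts -15 - (-25) = 10 min after the shift, as in the first SMS set. The CON row would end at -5 - (-25) = 20, against 15 in SMS, so the starts match but the ends need not.

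**Visit length and contrast.** The CON rows span 40 - (-30) = 70 min (75 stated). The SMS rows span 40 - (-140) = 180 (180 stated). With sitting from -25:00, CON spans 40 - (-40) = 80. The SMS-minus-CON difference in sitting is 120 - 10 = 110 min by the timetable and 120 - 20 = 100 by section 2.3.

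**The case against.** The strongest reply is that the consequence depends on which version governs. Under section 2.3 the VICORDER slot would open 10 minutes after the shift and there would be no baseline problem. The documents do not say which version prevails, and Figure 2, which may show it, is not available here. This stands, so the effect on the baseline is stated only as conditional on the timetable being followed.

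The second reply concerns the labels. The CON reading is labelled -5 and the first SMS reading -115. Set against sitting starts of -15 and -125, both fall 10 minutes after the shift. The brachial-femoral reading straight after the test has a one-minute row (00:00 to 1:00). A similar reading at -6:00 to -5:00 would therefore come 9 to 10 minutes after the shift, close to the SMS start of 10. This also largely stands: for the primary vascular outcome the mismatch could be slight. It is not assured, because -5:00 is when the test begins, brachial-femoral PWV is listed first of three segments, measurements are in triplicate, and ultrasound of three arteries shares the window.

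Third, no section requires 10 minutes of seated settling, and SMS ultrasound itself starts 5 minutes after the shift. Section 1 does say "Pooling of blood in the lower-limbs is the first cardiovascular disruption as a result of PS", but that concerns prolonged sitting and gives no time course for PWV in the first minutes. It makes a posture effect plausible and does not establish one.

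A reader might go further and infer that CON's stress response is contaminated by posture while SMS's is clean. The documents do not support this. The first SMS set is itself only 10 to 15 minutes after the shift, so SMS change from baseline may carry some posture effect too. A direct comparison of the conditions after stress does not use the pre-stress reading at all. Nor can a bias in m/s be derived, since the documents give neither the size of a posture transient nor how fast it fades.

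**Conclusion.** The inconsistency is established: CON sitting before the stressor is 20 minutes in section 2.3 and 10 in section 2.6, while SMS is 120 in both. It is not a counting convention, because the same subtraction reproduces the SMS figure exactly, and the clock times agree with the minute column.

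If the timetable is followed, CON's only pre-stress VICORDER reading lies 0 to 10 minutes after the posture shift, against 10 to 15 for the first SMS set and 110 to 120 for the second. A full three-segment set cannot be given the settling time of the first SMS set; this rests on the assumption that it takes 5 minutes, as in SMS. Any baseline mismatch is of unknown size and direction, and may be small if CON is read at the end of its window. The case for acting rests on the two versions of the control condition and the unequal settling time, not on an estimate of bias.

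**What to change.** Use the 20 minutes of section 2.3 in the CON timetable:
- anthropometrics -40:00 to -35:00 and supine rest -35:00 to -25:00, each 10 minutes earlier than now;
- sitting from -25:00;
- ultrasound -20:00 to -15:00;
- VICORDER from -15:00, with the test at -5:00 as now.

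This is the SMS pre-stress sequence. The stated CON visit time should be updated from 75 minutes to the 80 that the rows would span. The time-commitment table follows: its 255 minutes is 75 + 180 and would become 80 + 180 = 260, and the total 10 + 35 + 260 = 305.

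The cost is about 10 minutes more on one visit, with no added visits or measurements. The sitting contrast is 100 minutes rather than the timetable's 110, but 100 is what section 2.3 already describes. If 10 minutes is what the investigators intend, section 2.3 should be corrected instead and the shorter settling time justified.
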